### 1.1.3 Rationale for PD-L1 Inhibitor + Hypofractionated Radiotherapy (HFRT) in transformed *IDH* mutant GBM

Although there appears to be considerable rationale for the use of immune checkpoint inhibitors in gliomas, GBM tumors have a dominant immune suppressive microenvironment that may mediate intrinsic resistance. These mechanisms include secretion of immunosuppressive factors, expression of cell surface immunosuppressive factors such as PD-L1, and presence of immune cells that mediate immunosuppression such as tumor-associated macrophages of the M2 lineage and myeloid-derived suppressor cells (MDSCs). Indeed, highly variable efficacy has been reported with single agent immune checkpoint inhibitors in preclinical GBM models, with some studies reporting no efficacy.

One strategy to reverse the suppression of tumor immune responses involves the use of radiation therapy (RT), which has been shown to augment anti-cancer immune responses and enhance the efficacy of immune therapies in systemic cancer preclinical models and patients. Preclinical studies examining combined radiotherapy and checkpoint inhibition indicate that each activate mostly non-redundant immune stimulating mechanisms and the major contribution of radiotherapy appears to be increasing T-cell receptor (TCR) diversity. RT induces major histocompatibility complex (MHC) class I presentation, increases antigen presentation, and increases cytotoxic T cell (CTL) recognition of irradiated cells and enhances the diversity of the TCR repertoire of the expanded peripheral T cell clones. A recent study also demonstrated that fractionated radiotherapy leads to CD8+ T-cell-dependent adaptive upregulation of tumor cell PD-L1 expression.

CONFIDENTIAL

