In preclinical GBM models, the combination of immune checkpoint inhibition and a short course of RT has demonstrated impressive efficacy. RT induces a proinflammatory response to enhance the antitumor efficacy of immunotherapy. RT upregulates surface MHC class I expression, thereby enhancing the presentation of normally suppressed tumor-associated antigens, while also increasing ICAM-1 expression and CXCL16 secretion. RT also increases tumor-infiltrating lymphocytes (TILs), including 4 fold increases in total CD4+ and 4.5 fold increases in total CD8+ cells, and also mildly increases Natural Killer cell infiltration. Additionally, RT alone can decrease intratumoral Treg levels, and RT + anti-PD1 therapy synergize to increase cytotoxic T cell (CTL) infiltration and significantly increase the CTL to Treg ratio in the tumors. In orthotopic, syngeneic murine glioma models, combined immune checkpoint inhibitor and short course RT therapy cured a significant fraction of mice, generating robust antitumor immune responses, tumor regressions, long-term survival and antitumor immunity.

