## 4 Subject Selection and Withdrawal

### 4.1 Inclusion Criteria

1. Male or female subjects aged  $\geq 18$  years.
2. Documentation of *IDH1* or *IDH2* mutation in any tumor specimen.
3. Pathologic evidence (either diagnostic pathology slides or pathology report) of a diagnosis of WHO grade II or III glioma prior to treatment with temozolomide or PCV chemotherapy.
4. Histopathological evidence of glioblastoma (WHO grade IV) on a progressive tumor specimen after treatment with temozolomide or PCV chemotherapy. The diagnosis of glioblastoma must be confirmed on central review by a study-designated neuropathologist at NYULMC at screening. Exceptions to this eligibility include the following:
  - a. Any progressive glioma with *IDH1* or *IDH2* mutation, regardless of WHO grade, histopathological diagnosis, or prior therapy, will be eligible if the progressive tumor specimen is found to have one of the genetic alterations below:
    1.  $\geq 20$  somatic mutations per Mb by whole-exome sequencing
    2. High mutation burden or microsatellite instability (MSI) identified by Foundation Medicine panel next-generation sequencing (FoundationOne®, FoundationOne CDx™). Foundation Medicine's threshold for high mutation burden (HMB) in their panel NGS assays is  $\geq 20$  somatic mutations per Mb. Foundation Medicine's panel NGS assay has been validated by whole-exome and whole-genome sequencing to correlate tightly with tumor mutation burden ( $R^2 = 0.94$ ).
    3. Mutation in a mismatch repair gene or other genes known to be associated with hypermutator phenotypes or microsatellite instability, including but not limited to *MSH2*, *MSH6*, *MLH1*, *POLE*, *PMS2*, *POLD* as determined by validated methods.
    4. Microsatellite instability as identified by polymerase chain reaction (PCR) or other validated methods.
  - b. Progressive oligodendroglioma (with 1p/19q codeletion) that has hallmark histopathological features of glioblastoma (i.e. necrosis, pseudopalisading necrosis, or microvascular proliferation) is eligible as *IDH1/2* mutant, 1p/19q codeleted oligodendrogliomas that have progressed after chemotherapy have been shown to develop hypermutation phenotype.

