5. Availability of a paraffin-embedded or frozen tumor-tissue block with a minimum of 1 cm^2 of tumor surface area from a tissue specimen that demonstrates pathological transformation to glioblastoma (WHO grade IV) or a progressive specimen that harbors one of the genetic alterations specified in Inclusion Criteria 4a.
  - a. If a tumor block cannot be submitted, then 20 unstained slides (preferably 10 slides from two different tumor blocks from the same surgery) from the tumor specimen must be submitted.
6. Patients must have had treatment with temozolomide, lomustine (CCNU) or PCV [procarbazine, lomustine (CCNU), vincristine] chemotherapy prior to histopathologic transformation to glioblastoma or prior to identification of one of the genetic alterations specified in Inclusion Criteria 4a. Notes or records from the treating oncologist are required for documentation of treatment history. Prior treatment with at least one of the following chemotherapy schedules is required to be eligible:
  - a. At least one 6 week course of continuous daily temozolomide

CONFIDENTIAL

- b. At least six 28-day cycles given in one of the following schedules:
    1. Daily for 5 days of a 28-day cycle
    2. Daily for 21 days of a 28-day cycle
    3. Daily for 14 days of a 28-day cycle
    4. Alternating 7 days on/7 days per 28-day cycle
    5. Continuous daily dosing of a 28-day cycle.
  - c. Other schedules of temozolomide may be considered after discussion with the overall Principal Investigator.
  - d. At least 3 cycles of PCV or lomustine (CCNU) chemotherapy.
7. Patients who received anti-tumor therapy after histopathologic transformation to glioblastoma must have shown unequivocal radiographic evidence of tumor progression by contrast-enhanced MRI scan (or CT scan if MRI is contraindicated).
8. Patients must have had prior CNS radiotherapy for their glioma, including standard doses for low-grade or high-grade glioma as well as non-standard dose and fractionation, including hypofractionated regimens, stereotactic radiosurgery, etc.
9. Patients can have had any number of prior therapies, including but not limited to molecularly targeted therapies and anti-angiogenic therapies, however they must have had prior chemotherapy with either temozolomide or lomustine as per Eligibility Criteria 6.
10. Karnofsky performance status (**Attachment 2**) of  $\geq 60$ .

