### 6.10.1 Archival Tumor Specimen

Archival tumor tissue from a previous surgical resection that demonstrates histopathological evidence of transformation to glioblastoma (GBM, WHO grade IV) or genetic alteration as specified in the **Eligibility Criteria (Section 4.1)** must be submitted.

A paraffin-embedded or frozen tumor-tissue block with a minimum of 1 cm^2 surface area of viable tumor is required. The tumor block should contain at least 20% viable tumor, i.e., a representative H&E slide should show that at least 20% of the specimen contains viable tumor.

If a tumor block cannot be submitted, then twenty (20) unstained 5-micron slides (preferably 10 slides from two different tumor blocks from the same surgery) from the tumor specimen must be submitted.

Note, an archival tumor specimen from the prior lower-grade glioma tumor is not required.

Send archival tumor specimens for research to:

[name]  
Department of Pathology, NYU Langone Medical Center  
[name]  
[name]  
[name]  
[contact]  
[contact]  
[contact]  
[contact]

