### 3. Tumor Tissue Immunohistochemistry (IHC)

**Objectives:** To assess the association of PFS6 and:

- A) Tumor tissue PD-L1 expression,
- B) baseline density and subtype of TIL populations.

**A) Tumor cell programmed death-ligand 1 (PD-L1) expression:** We will assess the association of PFS6 with baseline membranous and diffuse tumor cell PD-L1 expression. Tumor PD-L1 has been associated with response to PD-1 inhibitor therapy in studies of other solid cancers (see Rationale and Background, **Section 1.1**) however the association of tumor tissue PD-L1 expression and response to anti-PD-1 or anti-PD-L1 therapy is unknown.

IHC staining of paraffin-embedded sections for PD-L1 will be performed on archived formalin-fixed paraffin-embedded archival tumor specimens as previously described. The IHC assay for PD-L1 will incorporate an anti-PD-L1 rabbit monoclonal antibody (clone 28-8), which was developed on an automated platform by Dako North America. Consecutive sections will be stained for PD-L1 and a negative control reagent to control for nonspecific staining. A sample will be deemed PD-L1 positive for membranous staining if  $\geq 5\%$  of tumor cells, in a minimum of 100 evaluable tumor cells, have observable PD-L1-positive staining at any intensity. Specificity of the 28-8 antibody clone has been extensively validated previously.

In addition, we will explore the association of Treg (CD4+CD25+FoxP3+) levels in tumor tissue and in circulation at baseline. Circulating Treg levels will be quantified as below, and tumor tissues will be stained for CD4 and FoxP3 to assess infiltrating Tregs.

**B) Tumor Infiltrating lymphocytes (TILs):** We will assess the density and subtype of TILs in baseline pre-treatment FFPE tumor tissue by IHC using markers such as CD3, CD4, CD8, CD56, FoxP3, and PD-1.

**If Post-treatment tumor tissue is available:** Additionally, if patients undergo tumor resections or biopsies during study therapy or after progression on HFRT + Avelumab, we will assess for changes in tumor tissue PD-L1 expression and TIL density and subtype after treatment with Avelumab + HFRT.

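### Tumour PD-L1, TIL and TCR values analysed as baseline come from archival tissue whose timing relative to prior radiotherapy is open, so their associations with PFS6 may be diluted or, under a further condition, spurious

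*Combined protocol and SAP*

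**What the plan says.** **Specimen.** Section 4.1, criterion 5, accepts tissue "from a tissue specimen that demonstrates pathological transformation to glioblastoma (WHO grade IV) or a progressive specimen that harbors one of the genetic alterations". Section 6.10.1 asks for "Archival tumor tissue from a previous surgical resection that demonstrates histopathological evidence of transformation to glioblastoma" or with a qualifying genetic alteration. Neither gives a date window or asks for the latest specimen.

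**Order of events.** Criterion 4 requires "Histopathological evidence of glioblastoma (WHO grade IV) on a progressive tumor specimen after treatment with temozolomide or PCV chemotherapy", which places the glioblastoma specimen after chemotherapy. Criterion 8 states that "Patients must have had prior CNS radiotherapy for their glioma", but not whether this came before or after the specimen. Criterion 7 says that "Patients who received anti-tumor therapy after histopathologic transformation to glioblastoma must have shown unequivocal radiographic evidence of tumor progression"; that progression is shown by imaging, not by new tissue. Criterion 9 sets no limit on prior lines.

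**Use of the tissue.** Attachment 7, Tumor Tissue Immunohistochemistry, states: "We will assess the association of PFS6 with baseline membranous and diffuse tumor cell PD-L1 expression". It treats TIL density in the same way, as does the whole-exome section for intratumoral TCR diversity. The Statistical Considerations for Correlative Studies contain no term for specimen date or intervening therapy.

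**Effect of radiotherapy.** Section 1.1.3 reports that "fractionated radiotherapy leads to CD8+ T-cell-dependent adaptive upregulation of tumor cell PD-L1 expression", and that radiotherapy increases tumour-infiltrating lymphocytes, "including 4 fold increases in total CD4+ and 4.5 fold increases in total CD8+ cells". It also says radiotherapy increases TCR diversity.

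**The concern.** Two quite different histories are eligible. One patient has chemotherapy, a glioblastoma specimen, radiotherapy, radiographic progression and then enrolment; the tissue predates the radiotherapy. Another is irradiated for a lower-grade tumour and re-resected shortly before entry (criterion 13 allows two weeks); the tissue follows it. Attachment 7 puts both on one scale. By contrast, the blood markers are fixed to within 3 days before C1D1 and the baseline MRI to within 14 days before the first dose.

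If radiotherapy moves the marker, the mixture adds variation unrelated to outcome, and a real association is harder to see. If specimen timing also tracks prognosis, for example through the number of lines given since the specimen, it can create an association where none exists. Tumour PD-L1 against PFS6 is a named secondary objective, and the plan also feeds the markers into combined logistic models to predict PFS6.

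**Working it through.** **1. The plan's own figure.** The only sizing behind the 43 patients is the Simon design in Section 7.1.3 (continue if at least 8 of 18, success if at least 23 of 43). The probability of success is the sum over x1 ≥ 8 of P(X1 = x1; 18, p) × P(X2 ≥ 23 − x1; 25, p). This gives 0.0474 at p = 0.40 and 0.8272 at p = 0.60, matching the stated 0.047 and 82.7%. Specimen timing does not enter this test. No power is stated for any biomarker.

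**2. Model for the illustration.** Take n = 43 and a log marker with SD 1, shifted by d in patients who achieve PFS6. For AUC 0.70, d = √2 × Φ⁻¹(0.70) = 0.742. Half the specimens predate radiotherapy; the others are higher by ln 2 = 0.693 or ln 4 = 1.386. The 4-fold value echoes the T-cell figure in Section 1.1.3. The half share, both shifts as applied to patients, and the PFS6 gaps below are assumptions.

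**3. Dilution, by hand.** With timing unrelated to PFS6, the AUC of the mixed marker is 0.5 × Φ(d/√2) + 0.25 × Φ((d + ln f)/√2) + 0.25 × Φ((d − ln f)/√2).
- 2-fold: 0.350 + 0.211 + 0.128 = 0.69
- 4-fold: 0.350 + 0.233 + 0.081 = 0.66

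**4. Dilution, simulated.** Two-sided Wilcoxon at 5%, at least 1,500 runs per scenario (standard error at most √(0.25/1500) = 1.3 points):

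| Specimens | Power |
|---|---|
| Uniform timing | about 62% |
| Mixed, 2-fold shift | about 57% |
| Mixed, 4-fold shift | about 46% |
| Mixed, 4-fold, linear model adjusted for timing | about 65% |

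If only 20% predate radiotherapy, the 4-fold figure is about 51%.

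**5. Out-of-date readings.** Suppose the old reading also correlates only 0.5 with the current value. With half the specimens old and a 4-fold shift, power is about 26% unadjusted and 42% adjusted. At correlation zero, adjusted power is about 21%.

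**6. Spurious association.** Set d = 0 and let PFS6 be 0.55 with post-radiotherapy and 0.35 with pre-radiotherapy tissue. The post-radiotherapy share is then 0.55/0.90 = 0.611 among patients who achieve PFS6 and 0.45/1.10 = 0.409 among the others. The expected log-marker difference is 0.202 × ln f, or 0.14 (2-fold) and 0.28 (4-fold), with no real effect. The simulated false-positive rate is about 7% and 11%, and about 5% after adjustment. With equal PFS6 in the two groups the difference is zero and the rate stays near 5%.

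**7. Binary marker as a cross-check.** Take true PFS6 of 75% versus 35% by current status, prevalence 50%, and Fisher's exact test. With all specimens current, the odds ratio is (0.75/0.25)/(0.35/0.65) = 5.6 and power about 70%. If 40% of readings are uninformative, PFS6 is 0.6 × 0.75 + 0.4 × 0.55 = 0.67 versus 0.6 × 0.35 + 0.4 × 0.55 = 0.43. The odds ratio is 2.7 and power about 28%. If instead radiotherapy turned half of the now-positive patients positive after those specimens were taken, power is about 49%.

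**The case against.** A reader might infer that the associations are diluted or spurious as a matter of fact. The documents do not support that.

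- **Share unknown.** Nothing says how many specimens predate radiotherapy. Criterion 8 counts radiotherapy at low-grade doses, so patients irradiated before transformation supply post-radiotherapy tissue. Nor can a specimen be wholly arbitrary in age: criteria 4 and 6 place it after chemotherapy.
- **Preclinical evidence.** The T-cell increases sit in a paragraph on preclinical glioblastoma models. The PD-L1 statement cites a study that Section 1.1.4 describes as a mouse colon cancer experiment. No fold change is given for PD-L1, the TCR text partly concerns peripheral clones, and nothing says the changes persist to enrolment, usually at least 6 months after radiotherapy.
- **Not a planned test.** Membranous PD-L1 is a positive/negative call at 5% of cells, and the plan for PD-L1 and TIL is mainly descriptive, plus logistic models. The Wilcoxon figures indicate scale; they are not the operating characteristics of a specified PD-L1 analysis.
- **Limited weight.** The correlatives are declared exploratory and unpowered. Of the three markers only PD-L1 is among the secondary objectives. Attachment 7 already calls the tissue archival in places, and pre-treatment is accurate relative to study treatment.

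All of this stands and limits the size. It does not remove the gap: the sponsor's own rationale says radiotherapy moves these markers, and the plan analyses tissue from either side of it as one time point. An adjustment chosen after the data are seen would also carry less weight than one written down now.

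**Conclusion.** The point holds in conditional form. Dilution requires that some specimens predate radiotherapy and that the marker shift is real in patients and lasting, or that old readings no longer reflect the tumour. A false association requires, in addition, that PFS6 differs by specimen timing; this is plausible through treatment history but not shown.

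Under the stated assumptions, the loss is about 5 points of power (2-fold shift) to 16 points (4-fold), more if old readings are also out of date. The false-positive rate is about 7% to 11% with a 20-point PFS6 gap by timing, and near 5% without one. If few specimens predate radiotherapy, or the shift is transient, the effect may be negligible.

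It would be wrong to extend this to the trial's main conclusion: the primary PFS6 test does not use the tissue markers. It would also be wrong to expect adjustment to repair everything, as step 5 of the working shows. Severity is minor to moderate.

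**What to change.** In Attachment 7, Statistical Considerations for Correlative Studies:

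1. Derive for each specimen its date and any radiotherapy or other anti-tumour therapy given between it and C1D1.
2. Include specimen taken before or after the last prior radiotherapy as a covariate in the PD-L1, TIL and tumour-TCR associations with PFS6.
3. Repeat these associations, as a sensitivity analysis, in patients with no intervening therapy.
4. Describe the values as archival rather than baseline.

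The pathology documents and oncology treatment records required at screening should already hold the inputs. Eligibility, visits and treatment do not change. The cost is some wording, one degree of freedom and a small sensitivity subset. In simulations with 20% or 50% pre-radiotherapy specimens, shifts of 1- to 4-fold and old-to-current correlations of 1, 0.5 and 0, the adjusted test never had less power than the unadjusted one. The text should state the limit: adjustment removes a shift between specimen types but does not restore information lost because an old specimen no longer represents the current tumour.

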**Exception Note:** Any progressive glioma with *IDH1* or *IDH2* mutation, regardless of WHO grade, histopathological diagnosis, or prior therapy, will be eligible if the progressive tumor specimen is found to have one of the genetic alterations associated with hypermutation phenotype per **Section 4.1, Inclusion Criteria 4a**. A molecular pathology report indicating an eligible genetic alteration is sufficient documentation for an eligible genetic alteration and central histopathologic review is not needed for this exception.

- Collection of archived tumor material for research: The subject will be asked to arrange to provide archival tumor tissue from a surgical resection that demonstrates histopathological evidence of glioblastoma (GBM, WHO grade IV) or a genetic alteration as specified in the **Eligibility Criteria (Section 4.1)**.
- Brain MRI (or CT if MRI is contraindicated): Contrast-enhanced brain MRI or CT must be performed within 14 days prior to the first dose of study treatment (Avelumab infusion)
- Medical history: The subject must be eligible by all of the **Subject Selection Criteria** per **Section 4**. Concomitant therapeutics will be reviewed for allowed or prohibited medications. Of note:
  - Subjects must have documentation (treating oncologist note or treatment summary) of treatment with temozolomide, CCNU or PCV chemotherapy for their glioma prior to the transformation to GBM as specified in the **Eligibility Criteria (Section 4.1)**.
  - Subjects who received anti-tumor therapy after histopathologic transformation to glioblastoma must have shown unequivocal radiographic evidence of tumor progression by contrast-enhanced MRI scan (or CT scan if MRI is contraindicated).

CONFIDENTIAL

- Chest x-ray: Chest x-ray is required at screening if not performed within 60 days prior to initiation of study treatment.

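### Criterion 7's proof-of-progression rule has no 4a clause, so a treated 4a entrant without glioblastoma histology can enrol with stable disease and be counted in the PFS6 test

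*Combined protocol and SAP*

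**What the plan says.** Section 4.1 of the combined protocol and SAP has a main entry route, histological transformation to glioblastoma after chemotherapy, and a genetic exception, 4a. Under 4a a progressive IDH-mutant glioma is accepted "regardless of WHO grade, histopathological diagnosis, or prior therapy, will be eligible if the progressive tumor specimen is found to have" one of the listed alterations.

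Two of the criteria that follow were adapted to this route:
- Criterion 5 (tissue) accepts a glioblastoma specimen "or a progressive specimen that harbors one of the genetic alterations specified in Inclusion Criteria 4a".
- Criterion 6 (prior chemotherapy) requires treatment before transformation "or prior to identification of one of the genetic alterations specified in Inclusion Criteria 4a".

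Criterion 7 was not adapted: "Patients who received anti-tumor therapy after histopathologic transformation to glioblastoma must have shown unequivocal radiographic evidence of tumor progression by contrast-enhanced MRI scan". The medical-history item in section 6.1 has the same trigger: "Subjects who received anti-tumor therapy after histopathologic transformation to glioblastoma must have shown unequivocal radiographic evidence of tumor progression". Footnote 6 of the Schedule of Events (Attachment 1) repeats it.

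On analysis, section 7.2.2 starts PFS at treatment initiation. Section 7.3.2 puts every subject with at least one avelumab dose in the primary analysis, with no separate 4a stratum. Section 7.1.1 takes the 40% benchmark from recurrent glioblastoma studies. Section 7.1.3 counts anyone not on treatment through six cycles as a failure.

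**The concern.** Criterion 7 ensures that a patient treated since transformation has failed that treatment before the PFS clock starts. For a 4a entrant who never had glioblastoma histology the trigger cannot fire, whatever therapy followed the qualifying specimen.

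A patient whose disease is controlled by that earlier therapy has a better chance of being progression-free at six months than a patient with active recurrence, even if the study treatment adds nothing. A single-arm test against a fixed null has no control group to absorb the difference, so the error runs towards declaring the regimen interesting. The patient would also be re-irradiated without documented progression since the last therapy, which criterion 7 rules out for those treated after transformation.

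**Working it through.** **Step 1: does another criterion close the gap?** Take a patient treated with an adequate temozolomide course for a grade II or III glioma. The recurrence is resected, is not glioblastoma, and carries a 4a alteration. The patient then has a first course of radiotherapy plus PCV and is stable for a year.

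| Section 4.1 criterion | What it asks | Stops this patient? |
|---|---|---|
| 4a | Progressive specimen with a listed alteration; no date limit | No |
| 5, 6 | Tissue, and chemotherapy before the 4a finding | No |
| 7 | Progression if treated after transformation | No, there was no transformation |
| 8, 9 | Prior radiotherapy; any number of prior therapies | No |
| 11 | Evidence of tumor or progression only if radiotherapy ended under 6 months ago | No |
| 12 | Washout periods only | No |

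The exclusions in section 4.2 contain no requirement for measurable or progressing disease. Section 6.9 and Attachment 3 require measurable disease only for response evaluability. The screening MRI in section 6.1 is mandatory, but nothing says it must show progression.

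**Step 2: reproduce the stated design.** Section 7.1.3 gives 18 patients in stage 1 (stop at 7 or fewer successes), 43 in total, and a positive result at 23 or more. With p the true PFS6:

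P(positive) = sum over x = 8 to 18 of Bin(x; 18, p) × P[Bin(25, p) ≥ 23 − x]

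- p = 0.40: 0.0474 (stated 0.047)
- p = 0.60: 0.8272 (stated 82.7%)

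The stated operating characteristics are correct.

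**Step 3: add stable entrants with no treatment effect.** Let f be the share of stable 4a entrants, q their PFS6, and b the PFS6 of everyone else. Then p = b(1 − f) + qf in both stages. The documents give neither f nor q, so both are assumptions. For example, f = 0.10, q = 0.80 and b = 0.40 give p = 0.36 + 0.08 = 0.44 and P(positive) = 0.128.

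| b | q | f = 5%: p | P(positive) | f = 10%: p | P(positive) |
|---|---|---|---|---|---|
| 0.40 | 0.60 | 0.410 | 6.2% | 0.420 | 8.0% |
| 0.40 | 0.70 | 0.415 | 7.1% | 0.430 | 10.2% |
| 0.40 | 0.80 | 0.420 | 8.0% | 0.440 | 12.8% |
| 0.35 | 0.60 | 0.3625 | 1.4% | 0.375 | 2.2% |
| 0.35 | 0.80 | 0.3725 | 2.0% | 0.395 | 4.1% |

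A 5% share of 43 is about 2 patients (0.05 × 43 = 2.15); a 10% share is about 4 (4.3). The b = 0.35 rows are included because most of the reference rates in section 7.1.1 lie below 40%: 9-25% for chemotherapy, 29% and 42.6% for bevacizumab, and 28-39% for re-irradiation.

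**The case against.** **Progressive may mean progressing now.** Criterion 4a speaks of a progressive glioma, which can be read as a condition on the patient's current disease. But the eligibility test is applied to the progressive specimen, with no date or imaging requirement. The main route in criterion 4 also requires a progressive specimen, and the authors still thought criterion 7 necessary there.

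**There is another gate.** Attachment 7 makes the genetic route contingent on approval by the overall Principal Investigator. This could stop some such patients. It is discretionary, absent from 4.1 and from the 6.1 exception note, and not a progression test.

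**Footnote 6 closes the route.** It says that all patients must have a glioblastoma diagnosis. Read literally, that excludes these patients, but it contradicts 4a and the 6.1 exception note. It is a second inconsistency and cannot be relied on as a safeguard.

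**Stable entrants are not automatic successes.** This stands. The off-treatment rule in section 7.1.3 turns toxicity and withdrawal into failures, which is why the range for q starts at 60%.

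**The case is narrow.** This also stands. It needs a non-glioblastoma 4a entrant, later therapy, sustained control, and an investigator willing to re-irradiate without progression, in a protocol framed around recurrent disease.

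A reader might infer that all 4a entrants escape criterion 7. They do not: one who transformed earlier and was treated afterwards is caught. A reader might also infer that oligodendrogliomas entering under 4b escape it. The text does not support that. If the 4b histology counts as transformation, criterion 7 applies. If it does not and there is no 4a alteration, the patient fails criterion 5. If there is a 4a alteration, the patient is simply a 4a entrant.

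**Conclusion.** The omission is real, and no other entry criterion closes it for a 4a entrant without glioblastoma histology who was treated after the qualifying specimen and is more than 6 months past radiotherapy. The bias is towards a positive trial.

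Its size cannot be established from the documents. With all other patients exactly at the 40% null and stable entrants at an assumed 60-80%, the false-positive rate goes from 4.7% to 6.2-8.0% at a 5% share and 8.0-12.8% at a 10% share. With the others at 35%, it stays below 5% at both shares (at most 2.0% and 4.1%).

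A reader might conclude that the type I error is certainly inflated and the design invalid. The documents do not support that: the stated design reproduces, and whether the nominal 5% is exceeded depends on the unknown share, the unknown PFS6 of these entrants and the true rate in everyone else. Should fix, with moderate confidence.

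**What to change.** Keep the existing trigger in criterion 7, its copy in section 6.1 and footnote 6 of the Schedule of Events, and make two insertions in each:
- after the reference to transformation: *or after the progressive specimen that qualifies them under criterion 4a*;
- after the reference to tumor progression: *after that therapy*.

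The clause should be added to the transformation trigger, not replace it. A rule tied only to the qualifying specimen would let through a glioblastoma patient treated between transformation and a later re-resection on which they qualify. Criterion 7 catches that patient today.

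In the same amendment, reconcile two statements with 4a and the 6.1 exception note: footnote 6's requirement that all patients have glioblastoma, and Attachment 7's condition of overall Principal Investigator approval.

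The cost is a short amendment: two insertions in each of three places, plus the two reconciliations. No new test is needed, because the screening MRI is already required. The downside is that a few 4a patients with stable disease would wait until they progress.
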